Physiologic and biochemical markers will be measured by trained study staff twice per week and twice per day on 1 work day and 1 non-working day per week, for a total of four measurements per week (see section 7 for details). Physiologic and biochemical markers to be measured include: high-sensitivity C-reactive protein, blood pressure, and reduced heart rate variability – data to be downloaded via a smart phone (associated with CVD), and pro/anti-inflammatory cytokines (i.e., interleukin (IL)-1b, -6, -8, -10, tumor necrosis factor (TNF)-α, and interferon (IFN)-γ), and epigenetic changes associated with cancer and/or inflammation (see Figure 1 below and section 7 for details).

[figure not shown]

Figure 1: DRIVe Phase 1 - participant recruitment, screening, testing, intervention timeline in years 1, 2, and 3.

Polycyclic aromatic hydrocarbon (PAH) exposures will also be assessed through measurements of the urinary metabolite 1 hydroxy pyrene. Drivers will be asked to give a urinary sample in the morning after several days of work. They will be provided with a 100 cc sterilized polypropylene container. (Urinalysis Cup Kit). This will be collected by the study team, protected from sunlight and transported to *BAIC* for storage in a -20 degree freezer. Samples will ultimately be analyzed using liquid chromatography-tandem mass spectrometry (LC-MS-MS) by collaborating facility City College of New York. PAH exposures will also be measured through PUF sampler sized 10 cm by 2.2 cm diameter (171). Drivers will monitor PAH through PUF sampler one work day every week. The PUF filter will be placed in the vehicle of the drivers at the beginning of their work shift and picked up at the end of their shift. The study team will transport the sampler to the collaborating facility City College of New York for analysis.

The study team will be trained on screening and recruitment procedures, downloading DataRam results on PM measurements, on fingerstick blood, salivary, and buccal swab sampling procedures, and on storage/handling of samples (e.g. shipping dangerous goods training). Samples collected will be transported immediately by study staff to NYU for storage and analysis. If any critical abnormal/irregular health measurements are identified in the process of data collection, study staff will be trained to refer participant to low-cost health services.

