Following informed consent, participants will be assigned a participant number and administered the Intake Assessment (Appendix B). Participant drivers will also be randomized to either the Intervention or Wait-list Control Groups, as described above. A convenient time and place will then be arranged to complete the informed consent and Intake. Driver pairs will participate in the study in approximately the same time frame to avoid seasonal differences in PM levels.

During consent procedures, participants will be informed that they will receive a \$200 incentive over the course of the study for their participation to account for the time commitment required of participants. This will be distributed as 4 weekly incentives totaling \$50.00 each, which can be viewed as compensating study participants \$7 each day for carrying around monitors throughout their daily lives and allowing us to conduct biologic assessments 2 days a week. All participants will also be informed that they will receive a HEPA air purifier. Given the intensity of the proposed study measurements and the

associated time required of participants, for which drivers could result in lost earnings, the \$200 incentive is commensurate with the degree of commitment demanded.

Consenting professionals will emphasize the need to meet with participants 2 days a week to conduct study testing, and will discuss and compile a list of 2-3 future meeting locations for data collection. Convenient locations may include enclosed taxi garages, taxi relief stands, semi-private spaces within public venues, MSKCC offices or our community partner locations. Staff will not conduct any assessments at a participant's home.

During the initial conversation between the investigator/research staff and the potential study participant, the potential participant may be asked to provide certain health information that is necessary to the recruitment and enrollment process. They will use the information provided by to confirm that the potential participant is eligible and to contact the participant regarding study enrollment. If the person turns out to be ineligible for the research study, the research staff will destroy all information collected on the patient during the initial conversation, except for any information that must be maintained for screening log purposes.

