For all participants, measurements for environmental, physiologic and biochemical markers will be taken twice a week, and twice per day for a total of four data collection time points per week. This will include one work day per week (on the last work day of their work week) and on 1 day per week off from work. On work days measurements will be taken both immediately before (to establish pre-work biological parameters) and immediately after their work shift, and on non-work days measurement will be taken at approximately the same times during their day(s) off. In addition, blood pressure will be measured, data on heart rate variability will be downloaded, and a blood sample will be taken from each participant via finger stick to provide for measures of inflammatory markers and changes in white blood cell profiles. Salivary cotinine levels will also be measured twice (once at Intake and at the halfway point) for all participants to assess any exposure to smoking or smokeless tobacco products. High sensitivity C-reactive protein will be measured once during Intake and again at end of the 1 month period of participation. Buccal swabs will also be taken once during Intake for all participants, to measure epigenetic changes associated with inflammation, cancer and heart disease. Measurements will take place at locations most convenient for participants. Locations may include enclosed taxi garages, taxi relief stands, semi-private spaces within public venues, MSKCC offices or our community partner locations. Staff will not conduct any assessments at a participant's home. All measurements will be collected by trained study staff including both IHCD research and outreach personnel. Samples will be collected and transported immediately to MSKCC Core facilities, located on the 4th floor of the Breast and Imaging Center for storage. Samples will be shipped to NYU facilities for processing by Dr(s) [name] and [name] (see Lab Manual for shipping details). Trained study research and outreach personnel will be handling the specimens.

*Please see Appendix 4 RSA guide/lab manual for full details on all procedures.

1. PM values (measured daily):

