5. **Serum cytokines and white blood cell profiles** (measured before and after work shift 1 work-day per week on week 1 and week 4): Serum cytokines (i.e., interleukin (IL)-1 β , -6, -8, -10, tumor necrosis factor (TNF)- α , and interferon (IFN)- γ) will be measured using dried blood spot sampling and MesoScale Discovery (MSD) immunoassay system (www.mesoscale.com). As done previously in collaboration with the EPA, a drop of blood will be spotted onto a commercial sampling paper and allowed to dry. The sampling paper will be labeled with study ID, date, and the initials of the person conducting the collection. The paper, along with other study samples, will be transported immediately to the BAIC Core facilities, 4th floor storage at -80 Freezer, until shipped on ice to our EPA collaborator, , for analyses. Blood samples for testing

will be obtained by punching a disc from the center of the spot, followed by a simple liquid extraction of the sample. MSD assays employ a sandwich immunoassay format whereby captured antibodies are coated in a single spot on the wells of a MULTI-SPOT plate. Multiplex assays can measure 1-10 cytokines in a 96-well MULTI SPOT plate; each sample will be analyzed in duplicate. A second blood drop from the finger stick will be placed onto a glass slide, air-dried, stored in a locked box for later H&E staining and used for differential counts of white blood cell profiles as a systemic marker of inflammation. Slides will be shipped to [name] at NYU for analysis. (See blood prick test procedures in appendix 4 for details).

6. **High sensitivity C-reactive protein *hs-CRP***: Similar to the processes described above, the blood sample for *hs-CRP* analysis will be a drop of blood spotted onto a commercial sampling paper and allowed to dry. The sampling paper will be labeled with study ID, date, and the initials of the person conducting the collection. The paper, along with other study samples, will be transported immediately to the BAIC Core facilities, 4th floor storage at -80 Freezer, for analyses. (See blood prick test procedures in appendix 4 for details).

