For each group, a correlation matrix will be constructed between the three components of the AUC outcomes described in Aim 1a and a set of physiologic and biochemical markers. Generally, Pearson's correlation coefficients will be sought. If preliminary analyses found the variables to be skewed, then Spearman's rank correlation coefficients will be calculated instead. The purpose of these correlation coefficients are to examine the associations between the environmental exposure to air pollutants and physiologic and biochemical markers. Point-biserial correlation coefficients will be sought between the continuous AUC summaries of PM data and other binary variables of interest (e.g., methylation). These correlation coefficients can be sorted in descending order to help identify the top candidates of physiologic and biochemical markers that are most likely to be associated with PM exposure. Care will be taken to match the variables by time, using the time stamps from the PM measurements and the date of biomarker serum collection. For example, the AUC of PM in the first week will be associated with serum cytokines measured during the first week. This work will have to be done in a post-hoc manner, after we have all data sources. Then we will evaluate the best strategies to link them together by time. It helps to have automatic time stamps by the PM measurement devices, which is likely to minimize coding errors and missing data.

Aim 2: To use a randomized wait-list controlled design to conduct a pilot study of whether a targeted intervention, installation of a portable car high-efficiency particulate air (HEPA) filter (to remove PM), results in a reduction of in-vehicle PM exposure and associated physiologic and biochemical markers among taxi drivers..

We will calculate the difference in the three PM components and in physiologic/biochemical markers between the HEPA intervention condition and the Wait-List Control condition to obtain the pilot data needed for a future, larger study with the potential to provide remediation to potential harmful exposures to air pollution among NYC taxi drivers.

Aim 3: To collect feasibility data on conducting the proposed randomized wait-list controlled pilot study among New York City taxi drivers.

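### The first hs-CRP sample is drawn at Intake, before any study PM is described as recorded, although shift-timed finger sticks are already planned in week 1

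*Combined protocol and SAP*

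**What the plan says.** **Timing of hs-CRP.** The general text of section 7.1 gives two draws: "High sensitivity C-reactive protein will be measured once during Intake and again at end of the 1 month period of participation". Section 6.0 places Intake after consent and says "A convenient time and place will then be arranged to complete the informed consent and Intake". Neither hs-CRP draw is tied to a shift, a work day or a clock time.

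**Specimen.** Item 6 of section 7.1 says the hs-CRP sample "will be a drop of blood spotted onto a commercial sampling paper and allowed to dry". Item 5 uses the same medium for cytokines.

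**Finger sticks already planned.** Item 5 has cytokines and white-cell profiles "measured before and after work shift 1 work-day per week on week 1 and week 4". The general text of section 7.1 puts the sampled work day at the close of the driver's work week.

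**PM recording and linkage.** Section 4.3 gives a monitor to each enrolled driver, and section 11.0 summarises 28 daily averages. No recording before Intake is described. For Aim 1b, section 11.0 says markers will be matched to PM by time and gives an example: "the AUC of PM in the first week will be associated with serum cytokines measured during the first week". The remaining linkage is left to post-hoc work.

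**Other statements of the hs-CRP schedule.** Section 4.3 has markers taken "twice per week and twice per day on 1 work day and 1 non-working day per week" and then says "Physiologic and biochemical markers to be measured include: high-sensitivity C-reactive protein, blood pressure", with details deferred to section 7. The time-point table at the end of section 7 marks hs-CRP at Intake only.

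**The concern.** Section 2.0 names hs-CRP as a marker for Aim 1b, and Aim 2 carries the same markers forward. Section 3.0 motivates it by its response to short-term PM exposure, so the exposure of interest is the one shortly before the blood is drawn. An Intake sample has no study PM before it, and careful linkage afterwards cannot supply data that were never recorded.

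The only other hs-CRP draw comes at the end of the month, when Intervention drivers have had the filter for about two weeks. In that arm, hs-CRP under unfiltered driving therefore cannot be related to measured preceding exposure. The plan already avoids this for cytokines, with the same type of blood spot, by sampling around a week-1 shift.

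**Working it through.** **Plan's own figure.** Section 11.0 goes from 14 recruited to 11 analysable per arm at 25% drop-out: 14 × (1 − 0.25) = 10.5, rounded up to 11. This reproduces.

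**Inputs for the count.** Two arms; 11 analysable drivers per arm (14 if none drop out); two hs-CRP draws per driver, as in the section 7.1 text; filter introduced after week 2 in the Intervention arm (section 4.2). One assumption is needed: monitoring starts after Intake and before the sampled work day of week 1. The documents do not state the interval between Intake and the first monitored day.

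**All samples.**
- Section 7.1 text, total: 2 arms × 11 drivers × 2 draws = 44. Preceded by study PM (end of month only): 2 × 11 × 1 = 22.
- hs-CRP read from one stick on the week-1 and one on the week-4 shift day: total 2 × 11 × 2 = 44, all preceded by study PM.
- With no drop-out: 28 of 56 now, 56 of 56 after the change.
- If the time-point table were followed: total 2 × 11 × 1 = 22, none preceded by study PM, and no change could be calculated.

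**Drivers with at least one hs-CRP value that is both unfiltered and preceded by study PM, at 11 per arm.**

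| Arm | Section 7.1 text | Week-1 and week-4 spots |
|---|---|---|
| Intervention | 0 (Intake precedes PM; end of month follows the filter) | about 11 (week 1) |
| Wait-list | about 11 (end of month) | about 11 (weeks 1 and 4) |

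**Precision within a group.** Section 11.0 builds a correlation matrix for each group, so n is about 11 per matrix. The Fisher 95% limits are tanh(atanh(r) ± 1.96/√(n − 3)). At r = 0.3 and n = 11: atanh(0.3) = 0.310 and 1.96/√8 = 0.693, giving tanh(−0.383) = −0.37 and tanh(1.003) = 0.76. Such an interval is wide wherever the blood is drawn. The change makes an analysis possible in one arm; it does not make it precise.

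**Aim 2.** The filter enters only after week 2, so an Intake value precedes it in every driver. Both arms follow the same hs-CRP schedule and were randomised. Differences in work state between the first and last draws are therefore expected to be similar across arms, adding variance to the change score without shifting the between-arm contrast.

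**The case against.** Several points on the other side are sound.

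- **Intake hs-CRP can still be linked to something.** Weeks 1 and 2 are monitored without filters in both arms, among drivers with at least three years at the wheel, and could stand in for habitual exposure. The plan already correlates one Intake-only marker, methylation, with PM. It would therefore be too strong to infer that the Intake value has no PM to link to: what it lacks is PM recorded before the draw. If Intake fell in week 1, the same-week rule could pair the two, but with exposure largely after the blood sample. That suits a short-term marker poorly.
- **Aim 1b is not restricted to unfiltered weeks.** About 22 drivers have an end-of-month value preceded by PM, so hs-CRP is not lost to Aim 1b as a whole. The zero applies to unfiltered conditions in the Intervention arm.
- **A gain in precision from n = 11 to n = 22 might be inferred.** The documents do not support this, because it needs pooled arms and the matrices are per group.
- **A biased Aim 2 comparison might be inferred from unmatched draws.** The documents do not show one. They leave the work state at each draw unspecified; they do not plan a mismatch. The end-of-month spot may fall at a week-4 visit, and the lab manual, which is not part of the text reviewed, may say more.
- **This is a descriptive, resource-limited pilot with many markers.** That limits the weight of the point. It does not remove the case for a change that costs one drop of blood.

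**Conclusion.** The point holds for Aim 1b. On the section 7.1 text, half of the hs-CRP samples (22 of 44 at 11 per arm) have no study PM before them, and the Intervention arm has no unfiltered hs-CRP value preceded by PM, against about 11 drivers if week-1 spots are used. For Aim 2 the Intake value remains a valid pre-filter baseline; the expected cost of unfixed work state is noise, which the documents give no means of quantifying.

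The counts rest on the two-draw schedule, on 11 analysable drivers per arm, and on monitoring starting between Intake and the week-1 shift day. The two-draw schedule is itself uncertain, because sections 4.3 and 7.1 and the time-point table disagree and must be reconciled. This is a worthwhile low-cost improvement to a secondary part of a pilot, and it does not undermine the study.

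**What to change.** - In the general text of section 7.1 and in item 6, take hs-CRP from the week-1 and week-4 work-day finger sticks at one fixed position, for example post-shift in both weeks.
- In section 11.0, Aim 1b, link each hs-CRP value to PM recorded up to that draw. For Aim 2, name week 1 as the hs-CRP baseline.
- State that monitoring begins before the week-1 sampled work day.
- In the same edit, reconcile the hs-CRP schedule across section 4.3 (among markers taken four times a week), the section 7.1 text (Intake and end of month) and the time-point table (Intake only).

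**Cost.** Protocol wording and one more drop at a stick already planned. Against the section 7.1 text, assays stay at two per driver. The Intake finger stick is no longer needed, since the other Intake specimens in the table are buccal and saliva. The downside is losing an hs-CRP value from before monitoring began, unless the Intake spot is kept as descriptive only, which would add a third assay per driver.

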4.1 OVERVIEW OF STUDY DESIGN/INTERVENTION

4.2 Design

This study is proposed to be carried out across a two year period including an intervention period and dissemination of results to the Taxi Network community. Twenty eight non-smoking male NYC cab drivers will be recruited and randomized to one of two study arms, an Intervention Group (to receive the HEPA filter 2 weeks into their 4 week period of participation) and a Wait-list Control Group (to receive the HEPA filter at the end of their 4 weeks of participation). For the Intervention and Wait-list Control Group drivers, during the first 2 weeks, measurements (e.g. biological markers and air monitoring) will be taken under usual conditions. At the end of the initial two weeks, portable HEPA air purifiers (136) will be placed in the Intervention Group drivers' cars and the air monitoring and biological parameters will be repeated for another 2-week period, to determine changes in PM levels and physiological measurements as a result of this targeted intervention. The Wait-list Control Group drivers will not receive a HEPA air purifier at this time, but will also have the air monitoring and biological parameters repeated for another 2 weeks. At the end of the 1 month period of measurements for both groups of drivers, the Wait-list drivers will then receive a HEPA air purifier, so that they may also potentially benefit from the intervention being tested in this study, but no further measurements will be taken. Drivers will serve as their own controls before/after work and before and after the intervention.

Our taxi network CAB (Community Advisory/Action Board) will be engaged in the implementation and dissemination of the proposed study. This Taxi CAB represents the full range of the taxi driver experience, including varied shifts, income, education, age, ownership/lease arrangements, and countries of origin. The Taxi CAB will be instrumental in study recruitment and dissemination of results. The CAB will meet quarterly, with additional meetings as needed. This study is conducted in collaboration with Drs. [name] and [name]'s research teams at New York University Department of Environmental Medicine, and [name], working from the City College of New York (CCNY). Biological specimens collected will be immediately transported to MSK BAIC Core facilities for temporary storage and will be shipped later to either NYU or CCNY (outlined in the assessment and evaluation-section 7).

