7. **Salivary cotinine** (measured at Intake and at the half-way point): Participants will be directed to use a saliva collection aid with a cryovial for collection of 1ml saliva sample. Saliva sample can only be collected at least one half hour after eating or drinking. Saliva samples will be frozen at -20°C. Cotinine will be measured with an EIA (Enzyme-immunoassay) (148). (See salivary cotinine test procedures in appendix 4 for details). Saliva samples will be transported to MSK BAIC Core facilities for temporary storage, until shipped to Drs. [name] and [name] at NYU for analysis.
8. **Epigenetic changes** (at Intake): We will use the minimally invasive buccal cell approach to identify traffic pollution-related epigenetic biomarkers in taxi drivers, because gene expression changes induced by inhaled pollutants in human subjects in buccal and/or nasal cells reflect those in bronchial epithelium (76, 149, 150). Buccal cells will be collected from study participants by gently scraping both left and right inner cheeks using special collection brushes (Gentra Puregene Buccal Cell Kit, Qiagen, Valencia CA). Methylation-specific PCR (MSP) (151) will be performed as routinely (134), using HotStar Taq DNA Polymerase kit (Qiagen), using MSP primers identified from the literature. Methylated (M) or unmethylated (U) status will be denoted per gene per participant. Buccal samples will be transported to MSK BAIC Core facilities for temporary storage and later shipped to collaborators at NYU for analysis. (See buccal swab test procedures in appendix 4 for details)

PAH (Polycyclic Aromatic Hydrocarbon) will be assessed via urine sample collection of Urinary 1 hydroxy pyrene and particulate matter collected via Polyurethane Foam Filter (PUF) sampler:

9. **PAH via Urinary 1 hydroxy pyrene**: Drivers will be asked to give a urinary sample twice during the study. The first urine sample will be collected on the morning at the end of the first or second work week of study. The second sample will be collected from drivers on the morning of the end of the fourth week of study participation. Drivers will be provided with a 100 cc sterilized

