Feasibility data will be collected to inform the conduct of a large scale randomized controlled trial assessing the impact of the HEPA filter intervention on reducing PM exposure and associated physiologic and biochemical markers. We will document the number of individuals approached for participation, the number refusing and reasons for refusal. We will document the time spent and the number of attempts to contact participants by phone and to meet in person. We will document adherence with study protocol, i.e. taking the dataRAMS to and from home and work, completing the multiple biological measurements. We will document the time spent conducting the study measurements. We will document dropout rates and reasons for drop out.

PARAMETERS-TIME POINTS*	At Intake	At Half-Way Point	1 Work Day per Week	1 Non-Work Day per week	1 work day (wk 1 & wk 4)	Every Day
Epigenetic Changes	X					
Hs-CRP	X					
Salivary Cotinine	X	X				
Serum Cytokines					X	
White blood cell profile					X	
Blood Pressure			X	X		
Heart rate variability						X
PM/Air Pollution						X
1-hydroxypyrene					X	
Black carbon			X			
PUF sample			X			

* Study Period = 28 Days

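### Section 7.1 contradicts itself on hs-CRP: the text plans a sample at the end of the month, the schedule table marks Intake only and so leaves no value after filter placement

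*Combined protocol and SAP*

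**What the plan says.** - **Section 7.1, text:** "High sensitivity C-reactive protein will be measured once during Intake and again at end of the 1 month period of participation".
- **Section 7.1, item 6 (hs-CRP):** describes the sample and its storage ("analysis will be a drop of blood spotted onto a commercial sampling paper and allowed to dry") but gives no time point.
- **Section 7.1, table of parameters and time points:** the hs-CRP row has a single mark, under Intake. Nothing is marked in the column headed "1 work day (wk 1 & wk 4"), and the table has no end-of-study column.
- **Section 7.1, neighbouring items:** cytokines are "measured before and after work shift 1 work-day per week on week 1 and week 4" and salivary cotinine is "measured at Intake and at the half-way point". The table agrees with the text for both.
- **Section 4.3:** gives a general frequency, "for a total of four measurements per week (see section 7 for details"), followed by a list: "Physiologic and biochemical markers to be measured include: high-sensitivity C-reactive protein, blood pressure, and reduced heart rate variability", then cytokines and epigenetic changes.
- **Section 4.2:** "At the end of the initial two weeks, portable HEPA air purifiers (136) will be placed in the Intervention Group" drivers' cars. Wait-list drivers receive theirs only after measurement ends.
- **Sections 2.0 and 11.0:** Aim 1b names hs-CRP as a marker of cardiovascular risk. Aim 2 plans a difference between the HEPA and wait-list arms in the physiologic and biochemical markers.

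**The concern.** Two current statements in one section give different sampling schedules for a named marker, and the item that should settle the matter is silent. The difference falls on the one sample that matters for the intervention question. The filter goes in halfway through the four weeks, so a marker measured only at Intake carries no information about it.

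If the table is what staff use in the field, the arms can be compared on hs-CRP only before either has been treated differently. Section 4.2 also has drivers act as their own controls before and after the intervention. With one value per driver that is impossible for hs-CRP, and the pilot would give a later trial neither an hs-CRP change nor its standard deviation.

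**Working it through.** **Inputs**

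- Drivers recruited: 14 per arm, two arms (Section 11.0), so 2 × 14 = 28.
- Analyzable drivers: 11 per arm after 25% drop-out (Section 11.0). Check: 14 × (1 − 0.25) = 10.5, which rounds to the plan's 11. Both arms: 2 × 11 = 22.
- Filter placement: end of week 2 of 4 (Section 4.2).
- hs-CRP time points: Intake and end of month (Section 7.1, text), or Intake only (Section 7.1, table).

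**Counts**

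Total values = time points per driver × drivers. Post-filter values = time points after week 2 × drivers.

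| Source in Section 7.1 | Values per driver | After week 2, per driver | Total, 28 drivers | After week 2, 28 drivers | After week 2, 22 analyzable |
|---|---|---|---|---|---|
| Text | 2 | 1 | 2 × 28 = 56 | 1 × 28 = 28 | 1 × 22 = 22 |
| Table | 1 | 0 | 1 × 28 = 28 | 0 | 0 |

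Extra assays if only the Intake sample was budgeted: 56 − 28 = 28.

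**Could the table's single mark be an artefact of how the file was read?** Probably not. Cotinine and blood pressure each keep two marks, and cytokines keep theirs in the column for weeks 1 and 4. The hs-CRP row has the same pattern as epigenetic changes, which the text really does place at Intake only. The likelier explanation is layout: with no end-of-study column, the second hs-CRP sample has nowhere to go.

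**Is a week-4 blood sample available anyway?** Yes. Item 5 schedules finger sticks before and after one work shift in week 4, and Section 7.1 puts the work-day visit on the last working day of the driver's week. An hs-CRP spot could come from one of those sticks.

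**The case against.** The strongest reply is that the text is explicit and the table is a summary. The table is loose elsewhere. It marks black carbon weekly although the stated minimum is one shift in each of weeks 1 and 4, and it puts urinary 1-hydroxypyrene under weeks 1 and 4 although item 9 allows the first sample in week 1 or week 2. Staff are also sent to the lab manual for procedures, and a Data Collection log is listed among the appendices. Neither is in the documents, and either may already give the right schedule. This stands as a limit on the likelihood of harm. It does not remove the contradiction.

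The stakes are also bounded. The analysis is descriptive, no test or power figure rests on hs-CRP, and Section 9.1 does not name it. Blood pressure, heart rate variability, cytokines, white-cell profile and 1-hydroxypyrene all keep post-filter values under the table. Aim 2 would lose one marker of several. That too stands, but a descriptive comparison still needs a value after the filter.

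A reader might go further and count Section 4.3 as a third schedule, with hs-CRP four times a week, or 4 × 4 = 16 values per driver. The documents do not support that. Section 4.3 gives a general visit frequency and refers to Section 7 for details. Its list also includes cytokines and epigenetic changes, which Section 7.1 places in weeks 1 and 4 and at Intake respectively, so it cannot be a marker-by-marker schedule.

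**Conclusion.** The point holds as a contradiction within Section 7.1: two hs-CRP values per driver with one after filter placement, against one value with none after. If the table governs, the post-filter count is 0 instead of 28 (22 analyzable), and the Aim 2 hs-CRP comparison is of pre-filter baselines only.

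The mismatch in the text is certain. The consequence is conditional: it assumes that staff follow the table over the sentence, and that the lab manual and Data Collection log do not correct it. The sentence is the more specific statement and probably the intent.

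A reader might also infer that a missed end-of-month value would be lost for good. The documents do not establish this. Week-4 blood for cytokines is spotted on paper and frozen, and nothing says whether leftover material could be assayed for hs-CRP.

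This is worth correcting before enrolment because following one of the two stated schedules would defeat a planned comparison, and the correction is small.

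**What to change.** 1. Keep the schedule in the text: Intake and end of month.
2. Add an end-of-month (week 4) hs-CRP mark to the table by a new column or a footnote. Do not use the existing column for weeks 1 and 4, since that would imply a week-1 sample that the text does not plan.
3. State in item 6 that hs-CRP is taken at Intake and at the end of week 4.
4. In both arms, take the week-4 spot from one named draw of the finger sticks already scheduled for cytokines, either pre-shift or post-shift and the same for every driver.
5. Make the lab manual and the Data Collection log match.

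Section 4.3 needs at most a tidy-up, since it already defers to Section 7. Reporting the hs-CRP arm difference as change from Intake is a reasonable option for Section 11.0, but resolving the schedule does not require it.

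Cost: one table column or footnote, a clause or two in item 6, and a check of the two appendices. No extra visit or finger stick is needed. At most 28 additional hs-CRP assays are required, and only if the Intake sample alone was budgeted.
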